5.0 METHODOLOGY

5.1 Entry Criteria

5.1.1 Diagnosis/Condition for Entry into the Trial

Melanoma.

5.1.2 Subject Inclusion Criteria

In order to be eligible for participation in this trial:

1. The subject must be informed of the investigational nature of this study and provide written informed consent in accordance with institutional and federal guidelines prior to study-specific procedures.
2. The subject must be ≥ 18 years of age on day of signing informed consent.
3. The subject must have biopsy proven or clinically documented advanced stage metastatic melanoma.
4. The subject must have measurable disease (per RECIST 1.1) that is seen on CT, MRI, or FDG PET/CT.
5. The subject must be recommended to start pembrolizumab.

5.1.3 Subject Exclusion Criteria

The subject must be excluded from participating in the trial if:

1. Females who are pregnant or breast-feeding at the time of screening will not be eligible for this study. Female participants of child-bearing potential will have a urine pregnancy test at the time of the screening visit.

2. Subject is not able to tolerate imaging procedures in the opinion of the investigator or treating physician.
3. Subject has a history or current evidence of any condition, therapy, or laboratory abnormality that might confound the results of the trial, interfere with the subject's participation for the full duration of the trial, or is not in the best interest of the subject to participate, in the opinion of the treating investigator.
4. Subject has received prior therapy with an anti-PD-1, anti-PD-L1, or anti-PD-L2 agent as assessed by medical record review and/or self-reported.
5. Subject has a known history of Human Immunodeficiency Virus (HIV) (HIV 1/2 antibodies) as determined by medical record review.
6. Subject has a diagnosis of immunodeficiency or is receiving systemic steroid therapy or any other form of immunosuppressive therapy within 7 days prior to the first dose of trial treatment.
7. Subject has known active Hepatitis B (e.g., HBsAg reactive) or Hepatitis C (e.g., HCV RNA [qualitative] is detected) as determined by medical record review.
8. Subject has known active central nervous system metastases and/or carcinomatous meningitis.

Note: Subjects with previously treated brain metastases will be eligible to participate provided they are stable (without evidence of progression by imaging for at least four weeks prior to receiving pembrolizumab and any neurologic symptoms have returned to baseline), have no evidence of new or enlarging brain metastases, and are not using steroids for at least 7 days prior to trial treatment.

5.2 Subject Recruitment and Screening

Patients will generally be offered enrollment at the time of their office visit to oncology at the Hospital of the University of Pennsylvania. Study personnel or an investigator will present the patient with information regarding the study and enrollment. Enrollment into the study will be presented as optional and will not impact clinical management or choice of therapeutic intervention. It will be emphasized that enrollment in the study is not mandatory and that failure to enroll will not result in prejudice by the treating clinicians and will not affect patient care.

All patients being considered for the study and eligible for screening must sign an informed consent for the study prior to any study specific procedures. Patients will generally have their baseline FDG PET/CT performed as a research scan. Occasionally, the baseline FDG PET/CT may be ordered by a treating physician as part of standard medical care, in which case the scan may occur before the patient is consented and enrolled in this study.

Information from this baseline FDG PET/CT scan will be compared to the post-therapy FDG PET/CT scans. FDG PET/CT scans performed at an institution outside of University of Pennsylvania health system will not be able to be used in this study.

5.3 Subject Withdrawal/Discontinuation Criteria

The criteria for enrollment must be followed explicitly. If a subject who does not meet enrollment criteria is inadvertently enrolled, that subject should be discontinued from the study. A subject may voluntarily discontinue participation in this study at any time. The investigator may also, at his or her discretion, discontinue the subject from participating in this study at any time. If a subject is prematurely discontinued from participation in the study for any reason, at any time, at either the investigator's discretion or the subject's request, an effort must be made to document the reason(s) why a subject fails to return to the study clinic for necessary visits or is discontinued from the study.

The primary reason for discontinuing participation in the study may include, but is not limited to, one of the following:

- The subject or legal representative (such as a parent or legal guardian) withdraws consent.
- Development of an intercurrent illness, injury, or medical condition likely to interfere with subject safety or the overall assessment.
- Noncompliance with protocol, e.g., the patient fails to appear at one or more imaging procedures.
- Development of any condition for which the investigator feels study withdrawal is justified.
- The subject has a confirmed positive serum pregnancy test
- The subject is lost to follow-up.
- Termination of the study.

Follow-up information will be obtained for subjects who discontinue the study. Additional details are listed in Section 7.1.4 (Visit Requirements).

Subjects may withdraw from the study at any time at their own request, or they may be withdrawn at any time at the discretion of the investigator or sponsor for safety, behavioral, or administrative reasons. If the subject withdraws from the study, and also withdraws consent for disclosure of future information, no further evaluations should be performed, and no additional data should be collected. The investigator may retain and continue to use any data collected before such withdrawal of consent.

6.0 TRIAL FLOW CHART

6.1 Study Flow Chart

	Screening Phase	Baseline FDG PET/CT ⁴	1 st Post-therapy FDG PET/CT	Tumor Tissue Collection ⁵	2 nd Post-therapy FDG PET/CT ⁶
Scheduling window relative to pembrolizumab initiation:		< 4 weeks prior	3 weeks after (\pm 3 weeks)		> 10 weeks after
Administrative Procedures					
Informed Consent	X				
Inclusion/Exclusion Criteria	X				
Demographics and Medical History	X				
Clinical Procedures/Assessments					
Review Adverse Events ¹			X	X	
Laboratory Procedures/Assessments: analysis performed on site					
Pregnancy Test – Urine or Serum β -HCG	X				
Tumor Imaging and Assessment of Disease					
FDG PET/CT ²		X	X		X
Tumor Biopsies/Archival Tissue Collection/Correlative Studies Blood					
Archival or Newly Obtained Tissue Collection	X			X	
Correlative Studies Blood Collection ³					

¹Adverse events related to the research PET/CT will only be assessed for the period of time from the injection of FDG to the completion of the imaging exam. AEs related to the clinical treatment will not be collected or reported as part of this study.

²All FDG PET/CT scans will be performed as per routine clinical procedure.

³Less than 65 mL of blood will be collected after initiation of pembrolizumab according to the following schedule: weeks 0, 1, 3, 6, 9, 12, 15, and at 1 year; specimens will be processed and stored according to the Penn Melanoma Program tissue collection Standard Operating Procedure. The week 1 blood sample will be collected only for the purposes of this study. If blood samples cannot be collected they will be omitted and not considered a protocol deviation.

⁴This scan will usually be performed as a research exam. Occasionally, it may be performed as a clinically indicated restaging exam, which may occur prior to consent and enrollment in this study.

⁵Tumor tissue is to be collected within 7 days after the 1st Post-therapy FDG PET/CT. The biopsy techniques preferred for this study include core biopsies or surgical biopsies. The same biopsy techniques should be used as routinely used for a given tumor lesion/location and specimens will be processed and stored according to the Penn Melanoma Program

tissue collection Standard Operating Procedure. When possible, the post-therapy tumor biopsy should target the same lesion that was biopsied pre-therapy; if the original lesion cannot be biopsied, then a lesion with a significant change in FDG activity should be targeted for biopsy. If patients have not consented to participate in the Penn Melanoma Tissue Collection Program, then a tumor biopsy will not be performed for the purposes of this study. In some patients the tumor biopsy may not be performed, or may be performed outside of the 7 day window following the 1st Post-therapy FDG PET/CT; omission/delay of the tumor biopsy will not be considered a protocol deviation.

⁶This scan is a clinically indicated restaging exam. In some cases MRI or CT imaging may be performed as standard of care for restaging disease instead of FDG PET/CT.

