3.2 Secondary Objectives & Hypotheses

(1) **Objective:** Based on changes in tumor FDG uptake at 3 weeks, determine which patients have FDG “flare” (an early increase in tumor FDG PET/CT uptake), and assess whether FDG “flare” is predictive of progression-free survival and overall survival in patients with melanoma on pembrolizumab.

Hypothesis: A flare response on FDG PET/CT performed 3 weeks after initiation of pembrolizumab is predictive of progression-free survival and overall survival in patients with melanoma.

(2) **Objective:** To collect tumor tissue pre- and post- treatment with pembrolizumab for correlation with changes in FDG uptake and objective response to therapy, and for studies of mechanism of action of PD-1 blockade with pembrolizumab.

Hypothesis: Treatment with pembrolizumab will result in a measurable change in tumor immune biomarkers, which will correlate with changes in tumor FDG uptake (including a “flare” response) and objective response to therapy, and will contribute to a better understanding of the mechanism of action of pembrolizumab.

(3) **Objective:** To measure immune biomarkers in blood from subjects before and at serial time points after treatment with pembrolizumab, for correlation with changes in FDG uptake and objective response to therapy, and for studies of mechanism of action of PD-1 blockade with pembrolizumab.

Hypothesis: Treatment with pembrolizumab will result in a measurable change in blood immune biomarkers, which will correlate with changes in tumor FDG uptake (including a “flare” response) and objective response to therapy, and will contribute to a better understanding of the mechanism of action of pembrolizumab.

(4) **Objective:** To correlate changes in tumor FDG uptake (including a “flare” response), serum immune biomarkers, and tissue immune biomarkers with objective response to therapy, progression-free survival, and overall survival. Changes in FDG uptake within immune related tissues (lymph nodes, spleen, bone marrow, and thymus) will also be correlated with serum and tissue immune biomarkers, and response.

Hypothesis: Serum and tissue immune biomarkers provide additional predictive value regarding objective response to therapy, progression-free survival, and overall survival when combined with FDG PET/CT imaging data.

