4.1.2.3 Biomarker Research

Almost all of the patients treated for melanoma in the University of Pennsylvania Health System (UPHS) have consented to participate in the Penn Melanoma Tissue Collection Program (UPCC #08607, IRB #703001). For patients participating in this program, blood samples will be collected, processed, and stored according to the program's standard operating procedure. Currently, this includes drawing less than 65 mL of blood according to the following schedule (after initiation of pembrolizumab): weeks 0, 3, 6, 9, 12, 15, and at 1 year. For the purposes of this study, patients will have an additional sample of blood drawn at approximately 1 week after starting pembrolizumab; this sample will also be collected, processed, and stored according to the Penn Melanoma Tissue Collection Program standard operating procedure. If patients have not consented to participate in the Penn Melanoma Tissue Collection Program, then no blood samples will be drawn for the purposes of this study. Analysis of blood samples will include, but is not limited to, analysis of serum cytokines, chemokines, and T cell markers. This data will be correlated to patient response as well as changes in tumor FDG uptake. Some of these studies will be performed upon receipt of additional funding. There may be patients for which some or all of these blood draws are not possible, in this case it will be documented in the CRF and the blood draws may be omitted and it will not be considered a protocol deviation. Experimental pathology results will not be reported to the participant and will have no impact on the treatment decisions made by the treating physician.

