7.1.2.3 Tumor Tissue Collection and Correlative Studies Blood Sampling

For patients participating in the Penn Melanoma Tissue Collection Program (UPCC #08607, IRB #703001), blood samples will be collected, processed, and stored according to the program's standard operating procedure. Currently, this includes drawing less than 65 mL of blood according to the following schedule (after initiation of pembrolizumab): weeks 0, 3, 6, 9, 12, 15, and at 1 year. For the purposes of this study, patients will have an additional sample of blood drawn at approximately 1 week after starting pembrolizumab; this sample will also be collected, processed, and stored according to the Penn Melanoma Tissue Collection Program standard operating procedure. If patients have not consented to participate in the Penn Melanoma Tissue Collection Program, then no blood samples will be drawn for the purposes of this study. Analysis of blood samples will include, but is not limited to, analysis of serum cytokines, chemokines, and T cell markers; proposed cytokines and chemokines are listed in Table 1, and proposed T cell markers are listed in Table 2. This data will be correlated to patient response as well as changes in tumor FDG uptake. Some of these studies will be performed upon receipt of additional funding. There may be patients for which some or all of these blood draws are not possible, in this case it will be documented in the CRF and the blood draws may be omitted and it will not be considered a protocol deviation. Experimental pathology results will not be reported to the participant and will have no impact on the treatment decisions made by the treating physician.

Patients may undergo tumor biopsy as part of their clinical care prior to initiation of pembrolizumab. For patients participating in the Penn Melanoma Tissue Collection Program, these pre-therapy tissue samples will be collected, processed, and stored according to the program's standard operating procedure. For the purposes of this study, patients will have a post-therapy tumor biopsy which will be scheduled within 7 days after the 1st Post-therapy

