This is a pilot correlative study of FDG PET/CT imaging to evaluate early response to immunotherapy. We will first begin with a descriptive analysis. For continuous variables, we will generate graphs and descriptive statistics (e.g., means, standard deviations, medians and inter-quartile range). Categorical variables will be described by frequencies, proportions and 95% exact confidence intervals. Change in tumor FDG uptake will be closely examined. It is likely that change in tumor SUVmax >20% will be classified as a FDG “flare” and the number of patients with a flare will be computed.

Next, associations between change in tumor FDG uptake with clinical outcomes will be conducted. Change in tumor FDG uptake at 3 weeks will be compared between responders and nonresponders by a two sample t-test. Also, objective response rates will be compared between patients with or without FDG “flare” by Fisher’s exact test.

PFS and OS will be estimated by the method of Kaplan and Meier. Median values and 95% confidence intervals will be calculated. PFS and OS will be compared between patients with or without FDG “flare” by the log rank test. Cox regression may be used to assess the effect of continuously scaled measurements of FDG change. For all survival analyses, a landmark analysis will be performed. Here, PFS or OS are defined from a landmark, which is 3 weeks after initiation of pembrolizumab. The landmark method is necessary because the change in tumor FDG uptake is known at 3 weeks. Serum and tissue biomarkers will be correlated with change tumor FDG uptake, using Pearson correlation or Spearman’s correlation, as appropriate. Within-patient pre-/post-treatment changes in biomarkers will be evaluated by paired Student’s t-test or Wilcoxon signed ranks test, as appropriate. We will test for an association between post-/pre-treatment fold change in immune biomarkers in serum and tissue and objective response, progression-free survival, and overall survival using logistic regression (for response) and Cox regression (for time-to-event outcomes) using landmark survival analysis.

8.5 Sample Size Justification:

The target is 30 evaluable patients, which may require up to 35 enrolled patients. Based on our clinical experience, we assume a 50% objective response rate, thus there will be 15

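### Change in serially drawn blood markers is tested only by pre/post paired tests, which lose power when draws are missed and can be biased at later visits if missingness follows the marker or the response

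*Combined protocol and SAP*

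**What the plan says.** Section 3.2, secondary objective 3, is explicitly longitudinal: "To measure immune biomarkers in blood from subjects before and at serial time points after treatment with pembrolizumab". Its hypothesis is that treatment produces a measurable change in blood markers, and that this change correlates with FDG change and with response.

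The flow chart in 6.1 (footnote 3) gives the schedule as "weeks 0, 1, 3, 6, 9, 12, 15, and at 1 year", which is one baseline draw and seven later ones. The same footnote allows for gaps: "If blood samples cannot be collected they will be omitted and not considered a protocol deviation". Section 4.1.2.3 expects them: "There may be patients for which some or all of these blood draws are not possible". Section 7.1.2.3 says how they are handled: "it will be documented in the CRF and the blood draws may be omitted and it will not be considered a protocol deviation". Patients outside the tissue program contribute nothing: "If patients have not consented to participate in the Penn Melanoma Tissue Collection Program, then no blood samples will be drawn".

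The analysis of change is one sentence in 8.4: "Within-patient pre-/post-treatment changes in biomarkers will be evaluated by paired Student’s t-test or Wilcoxon signed ranks test, as appropriate". The other biomarker analyses in 8.4 are correlations with FDG change, and logistic and landmark Cox models on a single post/pre fold change. Section 8 does not say which of the seven later draws is the post-treatment one. It contains no repeated-measures model, missing-data assumption or missing-data sensitivity analysis.

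**The concern.** The objective and the sampling are serial, but the test uses two draws at a time. A patient missing one of the two leaves that comparison, and a patient missing week 0 leaves every comparison. The patient's other draws carry information about the missing value and are not used.

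Two things are at stake. The first is power: with at most about 30 patients, each lost pair matters. The second is bias, which is conditional. If patients whose marker is moving the wrong way, or who are not responding, give fewer later samples, the remaining pairs are selected on something related to the quantity under test. The protocol's own hypothesis that marker change tracks response makes this plausible, but the documents do not show that it will happen.

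**Working it through.** **The plan's own figure.** The only power figure is in 8.5: 84% for FDG change, 15 responders v 15 nonresponders, a 1.0 SD difference, one-sided 5% t-test. With noncentrality 1.0 × √(15×15/30) = 2.74 on 28 df, power is 84.8%, so the figure reproduces. It does not concern the blood markers, for which no power is given.

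**Inputs.** From the documents: 30 evaluable patients, eight scheduled draws, 50% response. Assumed: all missing-draw rates, marker correlations and effect sizes. Marker values are in SD units.

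**1. Pairs lost when draws are missed at random.** With 15% of draws missed independently, the expected number of complete pairs is 30 × 0.85² = 21.7, about 22. At constant within-patient correlation 0.6, the SD of a change is √(2 × (1 − 0.6)) = 0.894, so a 0.5 SD change is 0.5/0.894 = 0.56 SDs of the change. Two-sided 5% paired power is 84% with 30 pairs and about 70% with 22.

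If the effect is instead 0.5 SD of the change itself:

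| Pairs missing | Pairs left | Paired power |
|---|---|---|
| 0% | 30 | 75% |
| 10% | 27 | 71% |
| 20% | 24 | 65% |
| 30% | 21 | 59% |
| 50% | 15 | 44% |

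In simulation with 15% of draws missed at random, a likelihood model on all draws had about 7 to 10 points more power than the paired test at weeks 3 to 12. Neither method was biased.

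**2. Drop-out that follows an earlier fall in the marker.** Assume 15% random misses plus drop-out averaging about 10% per visit, more likely after the marker has fallen, and no true change.

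| | Week 3 | Week 12 |
|---|---|---|
| Paired bias (SD) | about +0.03 to +0.04 | about +0.15 to +0.20 |
| Paired false-positive rate (nominal 5%) | about 6% | about 9% |
| Likelihood-model bias (SD) | about 0 | about 0 |

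About 14 pairs remain at week 12. The size depends on how steep the dependence is. A harsher version (four visits, about 19 final pairs, drop-out strongly tied to the last observed change) gave paired bias of +0.27 to +0.33 units, where the SD of change within a response group is about 1, and 22 to 25% rejection. The model's bias was again about zero.

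**3. Drop-out that follows response.** Let responders and nonresponders differ by δ in mean change, with half the patients in each group and fractions m_R and m_N of their pairs missing. The bias of the complete-pair mean is

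(δ/2) × [(1 − m_R) − (1 − m_N)] / [(1 − m_R) + (1 − m_N)].

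With δ = 1.0 SD and m_R = 10%:
- m_N = 30%: 0.5 × 0.20/1.60 = 0.06 SD
- m_N = 50%: 0.5 × 0.40/1.40 = 0.14 SD
- m_N = 70%: 0.5 × 0.60/1.20 = 0.25 SD

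The bias is zero if m_R = m_N or δ = 0. In simulation with response-driven drop-out, week-12 bias was about +0.20 SD for the paired test and +0.11 to +0.14 SD for a mixed model without response. The model reduces the bias but does not remove it, because response is only partly visible in the earlier marker values.

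**The case against.** The case for leaving the plan alone is substantial. Section 8.4 never names week 12 as the post-treatment draw, and what it does fix points to week 3: the landmark is 3 weeks and the main FDG change is at 3 weeks. Evaluable patients must have had the week 3 scan, which limits very early loss. At week 3 the simulated bias is small. The study calls itself a pilot, the blood work is secondary and partly depends on further funding, and 8.4 starts with graphs and descriptive statistics. A mixed model needs a covariance choice for each of many markers in a small sample, rests on its own missing-data assumption, and implicitly carries marker values beyond death.

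Most of this stands, and it limits the size and priority of the point. It does not remove it. The objective is written for serial time points, so later draws are part of the question, and the loss of power applies at week 3 too.

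Some stronger readings are tempting. A reader might infer that draws may be skipped at will, but the text covers draws that cannot be obtained and requires a CRF record. A reader might infer that the paired tests are biased as they stand, but that needs missingness related to marker change; otherwise only power is lost. A reader might also infer that a mixed model cures the problem, but it does so only when missingness depends on observed values.

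**Conclusion.** The point holds in a limited form. For a serial objective with expected gaps, 8.4 specifies only a two-draw test that discards incomplete pairs, although a better analysis of the same data is available.

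The better-supported cost is power: about 7 to 10 points for a 0.5 SD change if 15% of draws are missed at random. Bias is conditional and mainly affects later visits. It is about +0.15 to +0.20 SD at week 12 under marker-driven drop-out, with a false-positive rate near 9%, and little at week 3. The model removes that bias, but under response-driven drop-out it leaves about +0.11 to +0.14 SD against +0.20 SD for the paired test. Because no missing rate is documented, these figures illustrate what could happen and do not predict it.

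The documents do not support extending the point to the main results. The primary FDG objectives, the 84% power figure and evaluability do not depend on the blood draws. Low priority.

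**What to change.** In 8.4, for blood markers at weeks 0 to 15:

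- Make the main analysis of change one likelihood-based linear mixed model per marker, with visit as a categorical factor, within-patient correlation, small-sample degrees of freedom, and the log scale where suitable.
- Use every available draw, including those from patients with no week 0 sample.
- Report change from week 0 at each visit with a 95% CI and the number of patients contributing.
- Keep the paired t-test or signed-rank test as a sensitivity check, and for markers that the model does not fit.
- Add a sensitivity model with objective response as a term, because drop-out may follow response.
- Interpret visits after deaths have occurred as applying to patients still under observation, and report the 1-year draw descriptively.
- Keep the paired tests for tissue, which is sampled once before and once after treatment starts.

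The cost is some wording in 8.4 and slightly more analysis work, with no new samples or visits. The model needs a covariance choice and assumes that missingness depends on observed values; the plan should state both.
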